7.1.1.3. Multiparametric MRI

Statistical analysis comparing the subject group (HV or pSS patient) will be conducted for Multiparametric parameters (including but not limited to K_{trans} , D and f, as data permit), see Section 7.1.2 for detail. The median values of these parameters will be used for analysis.

Descriptive statistics will be calculated and presented graphically and in tabular format for multiparametric MRI quantitative derived parameters including but not limited to (median and IQR) K_{trans} , (median and IQR) ADC, (median and IQR) pure diffusion coefficient (D), and (median and IQR) microvascular fraction (f) as data permits. All parameters will be listed by group (HV or pSS patient) (and ROI, if data permits). When applicable for a given ROI, the analysis and summary outputs will be separated by the side of the ROI having higher parameter values and lower parameter values, as well as aggregated value. Aggregated measures (left-right combined) will use measures extracted over the combined ROI's, rather than left-right averages to not introduce a bias towards the smaller gland. As some of the MRI sequences may capture a reduced field-of-view of the salivary glands, the fraction of each gland that is analysed may be reported.

The data will be further explored using scatter plots and line plots to examine asymmetry in parameter values between left and right glands

Further details are given in [Appendix 11](#): List of Data Displays.

7.1.1.4. Comparison of pSS subjects with HV

An exploratory comparison of pSS vs HV may be performed for ¹¹C-MET PET/CT and multiparametric MRI derived parameters as data permit, to estimate a difference (or ratio if log transformation is needed) with 95% confidence interval obtained from the analysis described in Section [7.1.2](#).

7.1.2. Planned Imaging Statistical Analyses

Primary Statistical Analyses
Endpoint(s)

 • ¹¹C-MET PET/CT derived parameters, including but not limited to SUV_{peak}, SUV_{mean}, SUV_{max} • Multiparametric MRI derived parameters, including but not limited to (median and IQR) K_{trans}, (median and IQR) Pure diffusion coefficient (D), (median and IQR) microvascular volume fraction (f) and (median and IQR) ADC.
Model Specification

 • Parameters will be statistically analysed individually using an Analysis of Variance (ANOVA) model. • Terms fitted in the ANOVA model will include: Fixed categorical : Subject group (HV or pSS patient)
Model Checking & Diagnostics

 • Refer to Appendix 9: Model Checking and Diagnostics for Statistical Analyses : Model Checking and Diagnostics for Statistical Analyses.
Model Results Presentation

 • Estimates of Difference (pSS-HV) (or Ratio (pSS/HV) if log_e transformed) and 95% confidence interval for the derived parameters will be presented by ROI¹. • Plots of means (difference or ratio) and 95% confidence interval from the model will be generated for each ROI. • P-values will not be presented as formal hypothesis is not being tested. The interpretation will be based on point estimates and its precision (95% CI).

NOTES :

- [1]: When applicable for a given ROI, the analysis will be separated by the side of the ROI having higher parameter values and lower parameter values, and aggregated over both sides.

7.1.3. Bayesian Analysis

In addition, a Bayesian approach to the exploratory comparison of pSS vs HV analysis of the ¹¹C-MET PET/CT and multi-parametric MRI parameters will be used. The objective of this analysis is to allow interpretable probability statements for the difference in two groups.

For the endpoints defined in Section [7.1.2](#), the uncertainty of the endpoint will be described with probability density function p(μ), say, where ‘μ’ represents the parameter. P(μ) represents our ‘prior belief’, since very little is known about the distribution of such parameters, normal function is assumed to be suitable for the data. This will have an unknown mean and known variance taken from the raw data (i.e x_j~N(μ_j,σ_j²) where j is

the pSS patient group or the HV group). A weakly-informative (vague) conjugate Normal prior density function with mean zero and a large variance will be adopted for the group mean ($P(\mu)=N(0,100^2)$).

The endpoint from the study data will be used to gather evidence, which will be characterised via its likelihood function (derived from the relevant sampling distribution, $l(x|\mu)$, say, where 'x' stands for 'data' or in our case the parameter values).

This will lead to a Normal posterior density function for the endpoints of interest. Should the data not support a Normal likelihood function, alternative parametric forms, such as a log-Normal density, will be investigated.

Bayes' theorem will be applied to derive the posterior density function $p(\mu_j, x_j)$. PROC MCMC will be used for the analysis in SAS. The number of burn-in iterations will be at least 10,000 and the number of MCMC iterations, excluding the burn-in iterations will be at least 5000.

The posterior distribution for each endpoint will be summarised by region and group, including mean, median, SD, interquartile range and 95% credible interval based on highest posterior density (HPD) interval.

Samples from the posterior distribution for the group mean $p(\mu_j, x_j)$ for the pSS patients and for the HV subjects will be used to determine the posterior distribution for the ratio and difference of group means (pSS patients to the HV subjects). The posterior distribution for the ratio and difference of group means will be summarised by region and endpoint. Plots for the mean and 95% credible interval for the posterior distribution of the group mean and the difference of group means will be presented for each endpoint and region. Samples from the posterior distribution of the ratio of group means will be used to determine the probability that the ratio of the endpoints in pSS patients to HV subjects exceed 1 for each endpoint and region. This will be repeated for other values to allow us to plot a graph of probability of exceeding a certain value, for ratios of 1, 1.5 and 2. The ratio will be given such that group expected to have lower uptake will be used at the reference (denominator).

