#### **Group A: Healthy Volunteers:**

Approximately 4 to 12 subjects will be recruited. After approximately 4 subjects have been scanned, the variability in the imaging parameters will be assessed, after which up to 8 additional subjects may be recruited as following: a maximum of an additional 4 for  $^{11}\text{C}$ -MET PET/CT plus MRI (total maximum of 8 subjects for  $^{11}\text{C}$ -MET PET/CT), with the option for 4 extra for MRI only (total maximum of approximately 12 subjects for MRI).

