11.9. Appendix 9: Model Checking and Diagnostics for Statistical Analyses

11.9.1. Statistical Analysis Assumptions

Endpoint(s)	
 • ¹¹C-MET PET/CT parameters including but not limited to SUV_{peak}, SUV_{max} and SUV_{mean}. • Multiparametric MRI parameters including but not limited to diffusivity (D), microvascular volume fraction (f) and K_{trans}. • Additional quantitative parameters, if deemed appropriate.
Analysis	
 • Analysis of Variance (ANOVA) • Distributional assumptions underlying the model used for analysis will be examined by obtaining a normal probability plot of the residuals and a plot of the residuals versus the fitted values (i.e. checking the normality assumption and constant variance assumption of the model respectively) to gain confidence that the model assumptions are reasonable. • If there are any departures from the distributional assumptions, alternative models will be explored using appropriate transformed data. Mann-Whitney U test will also be used when untransformed data cannot be assumed to be normal.
Endpoint(s)	
 • Correlation between imaging parameters with 
 ○ other imaging parameters ○ salivary and tear flow ○ histological scores ○ disease activity ○ lab biomarkers of disease activity
Analysis	
 • Pearson Correlation Coefficient • Both variables should be normally distributed • Linear relationship between each of the two variables • Homoscedasticity of the data – equally distributed about the regression line. • Alternative, non-parametric method such as Spearman rank correlation will also be reported if assumptions are violated.

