11.12. Appendix 12: Example Mock Shells for Data Displays

Example : EFF_T1
 Protocol : 203818
 Population : Safety

Page 1 of n

Table 2.1
 Summary of ¹⁸F-FDG PET/CT parameters

Parameter: Parameter 1

Region of Interest	Sides	Group	N	n	Mean	SD	SE	Q1	Median	Q3	Min.	Max.
ROI 1	Low	pSS	xx	xx	xx.x	xx.xx	xx.xx	xx.x	xx.x	xx.x	xx	xx
		HV	xx	xx	xx.x	xx.xx	xx.xx	xx.x	xx.x	xx.x	xx	xx
	High	pSS	xx	xx	xx.x	xx.xx	xx.xx	xx.x	xx.x	xx.x	xx	xx
		HV	xx	xx	xx.x	xx.xx	xx.xx	xx.x	xx.x	xx.x	xx	xx
ROI 2	NA	pSS	Xx	Xx	xx.x	xx.xx	xx.xx	xx.x	xx.x	xx.x	xx	Xx
			xx	xx	xx.x	xx.x						

Note: NA: Sides are not applicable for all ROI.

Programming Note: Include Groups as a separate column next to Sides for 11C-MET PET/CT parameters summary.

Example : EFF_T2
Protocol : 203818
Population : Safety

Page 1 of n

Table X.X

Summary of Disease Activity (pSS only)

Disease Activity	N	n	Mean	SD	Median	Minimum	Maximum
------------------	---	---	------	----	--------	---------	---------

ESSDAI score

ESSRPI score

Patient Global assessment (VAS)

Physician Global Assessment (VAS)

Oral dryness numerical rating

Ocular dryness numerical rating

Example : EFF_T3
 Protocol : 203818
 Population : Safety

Page 1 of n

Table x.x

Summary of Correlation Between Disease Activity and Imaging Parameters

Disease Activity: [name of index]

Scan / Parameter	Side	Pearson's correlation / 95% CI	Spearman's correlation / 95% CI
¹¹ C-MET / SUVpeak	High	x.xx / (x.xx, x.xx)	x.xx / (x.xx, x.xx)
	Low	x.xx / (x.xx, x.xx)	x.xx / (x.xx, x.xx)
F-FDG / SUVpeak	High	x.xx / (x.xx, x.xx)	x.xx / (x.xx, x.xx)
	Low	x.xx / (x.xx, x.xx)	x.xx / (x.xx, x.xx)
MRI / Ktrans	High	x.xx / (x.xx, x.xx)	x.xx / (x.xx, x.xx)
	Low	x.xx / (x.xx, x.xx)	x.xx / (x.xx, x.xx)

Example: EFF_T4
Protocol: 203818
Population: Safety

Table x.xx

Point estimate and 95% CI for [imaging method] Derived Parameter of Difference in pSS vs. HV
95% CI for

ROI: [] Side: []

N	Group	n	Mean	Standard Error	Difference from HV	Difference (Lower, Upper)
xx	HV	xx	x.xx	x.xxx		
xx	pSS	xx	x.xx	x.xxx	x.xx	(x.xx, x.xx)
xx	HV	xx	x.xx	x.xxx		
xx	pSS	xx	x.xx	x.xxx	x.xx	(x.xx, x.xx)

Example: EFF_T5
 Protocol: 203818
 Population: Safety

Summary of the Posterior Distribution of the Ratio and Difference of Group Means for [Imaging method] parameters by Region

Parameter	ROI	Group	Prior Distribution for Θ	Value of σ used in the model	Posterior distribution					
					Mean	SD	Median	25th quartile	75th quartile	95% Credible Interval

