Mean SUV	Parotid Gland	pSS (N=xx)	normal(0, sd = 100)	1	x.xx	x.xx	x.xx	x.xx	x.xx	(x.xx,x.xx)
		HV (N=xx)	normal(0, sd = 100)	1	x.xx	x.xx	x.xx	x.xx	x.xx	(x.xx,x.xx)
		Difference			x.xx	x.xx	x.xx	x.xx	x.xx	(x.xx,x.xx)
		Ratio			x.xx	x.xx	x.xx	x.xx	x.xx	(x.xx,x.xx)
	Submandibular Gland									

pSS=primary Sjogren's Syndrome patients HV=Health Volunteers, ROI = Region of Interest

CONFIDENTIAL

203818

Number of MCMC iterations, excluding the burn-in iterations = 5,000. Number of burn-in iterations = 10,000
The PET parameters are assumed to follow a normal distribution with unknown mean Θ and known variance σ^2 (i.e. $N(\Theta, \sigma^2)$).
Difference calculated as pSS-HV and ratio as pSS/HV. 95% credible intervals based on the highest posterior density interval.

Example: EFF_T6
Protocol: 203818
Population: Safety

Page 1 of n

Posterior Probability that the Ratio and Difference of Group Means for [Imaging Method] Parameter Exceeds a Certain Value, by Region

Parameter (units)	Region	P(ratio) > 0.5	P(ratio) > 1	P(ratio) > 1.5	P(Difference) > 0
Mean SUV					

Note: P(ratio) > 1 is the probability that the posterior ratio of group means exceeds 1 based on 5,000 simulated posterior predicted values. *Ratio of pSS patients to Healthy Volunteers and difference of pSS-HV.*

Example : EFF_T7
 Protocol : 203818
 Population : Safety

Page 1 of n

Table X.X
 Summary of ESSDAI Component Scores
 Activity Level

Domain	No	Low	Moderate	High
Constitutional	n(%)	n(%)	n(%)	NA
Lymphadenopathy	n(%)	n(%)	n(%)	n(%)
Glandular	n(%)	n(%)	n(%)	NA
Articular	n(%)	n(%)	n(%)	n(%)
Cutaneous	n(%)	n(%)	n(%)	n(%)
Pulmonary	n(%)	n(%)	n(%)	n(%)

CONFIDENTIAL

203818

Renal	n(%)	n(%)	n(%)	n(%)
Muscular	n(%)	n(%)	n(%)	n(%)
PNS	n(%)	n(%)	n(%)	n(%)
CNS	n(%)	NA	n(%)	n(%)
Haematological	n(%)	n(%)	n(%)	n(%)
Biological	n(%)	n(%)	n(%)	NA

Example : EFF_L1
Protocol : 203818
Population : Safety

Listing xx
Listing of ¹⁸F-FDG PET/CT Parameters

Imaging Parameter

Subject	ROI	SUV _{mean}	SUV _{peak}	SUV _{max}	TR	TIV
xxxxx	Parotid Left					
	Parotid Right					
					

SUV= Standardised Uptake Value, TR = tissue-to-reference ratio ,TIV = total inflammatory volume.(description of all Parameter)

Example : EFF_L2
Protocol : 203818
Population : Safety

Page 1 of n

Listing No. XX

Listing of Tracer and Contrast Agent Administration Volume

Subjid	Visit	Contrast Agent/Tracer	Volume of Administration (Unit)
xxx	Visit1	Gadolinium	x
	Visit1	C-MET	x
	Visit2	FDG	x

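### The Bayesian pSS–HV analysis treats an SD estimated from 4–12 subjects as known, so its 95% credible intervals for the difference cover about 90–93% with 4 healthy volunteers and 92–94% with 8 or 12

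*SAP*

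**What the plan says.** SAP 7.1.3 supplements the ANOVA of 7.1.2 with a Bayesian analysis of the same ¹¹C-MET and MRI parameters. Its stated purpose: "The objective of this analysis is to allow interpretable probability statements for the difference in two groups". Each group's data are Normal with mean μ_j and variance σ_j², and of this distribution the SAP says: "This will have an unknown mean and known variance taken from the raw data". The prior, N(0, 100²), is on μ_j only, and the section states that a Normal posterior results. Posteriors are to be summarised "including mean, median, SD, interquartile range and 95% credible interval based on highest posterior density (HPD) interval".

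The ratio of means is handled as follows: "Samples from the posterior distribution of the ratio of group means will be used to determine the probability that the ratio" exceeds 1, with 1.5 and 2 to follow.

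Mock shell EFF_T5 (SAP 11.12) confirms the fixed variance. It has a column for the value of σ "used in the model", and its footnote begins "The PET parameters are assumed to follow a normal distribution with unknown mean" and goes on to call the variance known.

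On numbers, Protocol 9.2 says of the healthy volunteers: "After approximately 4 subjects have been scanned, the variability in the imaging parameters will be assessed", after which more may be recruited. The SAP synopsis gives 4 as the minimum. HV can therefore stay at about 4, with a ceiling of 8 for PET/CT and 12 for MRI; pSS runs from 8 to 12.

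**The concern.** A sample SD from 4 to 12 subjects is a noisy estimate. Fixing it in the likelihood removes that uncertainty from the posterior, so probability statements about the group difference come out too certain, most of all if HV stays at 4.

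The two documents also disagree. Protocol 4.3 says very little is known about the variability of these parameters and bases the sample size on reviewing it; SAP 7.1.3 then treats it as known. The ANOVA in 7.1.2 estimates its residual variance.

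A reader comparing the two analyses of one contrast would see a narrower Bayesian interval and credit it with extra information, although the prior supplies none.

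Nothing elsewhere in the SAP corrects this. Appendix 9 (11.9.1) says "Distributional assumptions underlying the model used for analysis will be examined by obtaining a normal probability plot of the residuals", but it covers the ANOVA and the correlations, not the Bayesian model. The log-Normal fallback in 7.1.3 changes the distribution without putting a prior on σ.

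**Working it through.** **Inputs.** HV n = 4, 8 or 12 and pSS n = 8 or 12 (Protocol 9.2). Prior N(0, 100²) and 95% HPD interval (SAP 7.1.3). The only pSS/HV SD ratio in the documents is for Ktrans: 0.05/0.04 = 1.25 (Protocol 9.2, literature table). Ratios from 1 to 2 are assumed around it, since the protocol expects greater variability among patients.

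**1. Reproduce Protocol Table 5 (SD = 1).** Half-width = t(0.975, n−1) × SD/√n:

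| n | t version | z version, 1.96/√n | Table 5 |
|---|---|---|---|
| 4 | 3.182/2 = 1.591 | 0.980 | 1.59 |
| 8 | 2.365/2.828 = 0.836 | 0.693 | 0.84 |
| 12 | 2.201/3.464 = 0.635 | 0.566 | 0.64 |

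The protocol's precision figures treat the SD as estimated. The known-variance version is 38%, 17% and 11% narrower (z/t = 0.616, 0.829, 0.890).

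**2. What the planned model gives.** Posterior precision of μ_j is n/s² + 1/100². At the protocol's MET SD of 1.5 and n = 4, that is 4/2.25 + 0.0001 = 1.778 + 0.0001, so the prior is negligible on this scale. The posterior is N(x̄, s²/n), and its 95% HPD interval is x̄ ± 1.96 s/√n. For the difference it is d ± 1.96 √(s₁²/n₁ + s₂²/n₂).

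**3. Coverage for one group mean.** P(|t with n−1 df| < 1.96) = 85.5%, 90.9% and 92.4% at n = 4, 8 and 12.

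**4. Coverage for the difference.** The interval in step 2 was integrated numerically over the two independent chi-square variance estimates. Simulation with 400,000 trials agreed within 0.1 point.

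| HV v pSS | ratio 1 | 1.25 | 1.5 | 2 |
|---|---|---|---|---|
| 4 v 8 | 90.8% | 91.5% | 91.9% | 92.1% |
| 4 v 12 | 90.2% | 91.2% | 91.8% | 92.6% |
| 8 v 8 | 93.0% | 92.9% | 92.7% | 92.3% |
| 8 v 12 | 93.2% | 93.4% | 93.4% | 93.4% |
| 12 v 8 (MRI) | 93.2% | 92.9% | 92.6% | 92.1% |
| 12 v 12 (MRI) | 93.7% | 93.7% | 93.6% | 93.3% |

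**5. Posterior probabilities.** With no true difference, P(difference > 0) exceeds 0.975 in (100 − coverage)/2 percent of trials. With 4 HV this runs from (100 − 92.6)/2 = 3.7% to (100 − 90.2)/2 = 4.9%. With 8 or 12 HV it runs from (100 − 93.7)/2, about 3.2%, to (100 − 92.1)/2, about 4.0%. The nominal rate is 2.5%. The 0.975 cut-off is illustrative; the SAP sets none.

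**6. Against the SAP's own ANOVA interval (both SDs 1).**
- 4 v 8: 1.96 × √(1/4 + 1/8) = 1.20, against 2.228 × 0.612 = 1.36
- 8 v 8: 1.96 × 0.5 = 0.98, against 2.145 × 0.5 = 1.07
- 12 v 12: 1.96 × 0.408 = 0.80, against 2.074 × 0.408 = 0.85

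**The case against.** The strongest reply is that 7.1.3 is supplementary. The ANOVA already gives a t-based interval for the same parameters, no hypothesis or threshold is attached, and EFF_T5 tells readers that the variance was taken as known. All of that is true and limits the harm to interpretation. But disclosing σ does not calibrate the interval, and in a study that withholds p-values and rests on estimates and their precision, interval width is the result.

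Coverage near 90% also needs HV to stop at 4 and depends on the SD ratio. That stands too: with 8 or 12 HV the shortfall is about 1 to 3 points. Ratios below 1 are worse: at 0.5, with 4 HV and 12 pSS, coverage is 87.5%.

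Two technical limits hold. The ratio of means does not have a z-interval, so the coverage figures apply to means and differences only. And the SAP gives no units for ADC, D or gland volume, so the vagueness of N(0, 100²) is not verified for those.

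The last objection is to the remedy. Separate flat priors on log σ_j make the intervals conservative, whereas one common σ would match the ANOVA and cover about 95.0% at equal SDs. That is a defensible alternative if specified in advance. However, it abandons the plan's group-specific σ_j, and it covers only 91.2% with 12 HV, 8 pSS and an SD ratio of 2.

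**Conclusion.** The concern holds. As specified, the nominal 95% credible interval for pSS minus HV covers 90.2–92.6% if HV stays at 4 and 92.1–93.7% with 8 or 12 HV; the single-group intervals are worse. These figures assume Normal data, SD ratios of 1 to 2, a sample variance with divisor n−1, and a parameter scale on which the prior is vague. Divisor n would lower coverage to about 87–93% at equal SDs.

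The plan should be corrected before database freeze. The error does not threaten a formal conclusion, because there is none, but it defeats the stated purpose of the section.

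**What to change.** 1. In SAP 7.1.3 and the EFF_T5 footnote, replace the known variance with an unknown σ_j sampled jointly with μ_j in the planned PROC MCMC step, and do the same for the log-Normal fallback. A flat prior on log σ_j gives each mean a t posterior with n−1 degrees of freedom and so reproduces Table 5. A weakly informative prior is also possible if its scale is stated for each parameter; a half-t prior would not reproduce Table 5 and depends on its scale at n = 4.
2. Remove the EFF_T5 column for the σ value.
3. For the ratio of means, report the posterior median, a quantile-based interval and the planned exceedance probabilities. Drop its posterior mean, SD and HPD interval.

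Step 3 follows from step 1: with 4 HV, the heavier-tailed posterior for the HV mean can cross zero in the denominator. The check took the ratio as pSS/HV, as in the EFF_T5 footnote, with the protocol's MET values for HV (6.00, SD 1.5) and an assumed pSS mean of 4.5 and SD of 1.5. The posterior SD of the ratio then ran from 0.13 to 17 across simulated trials (5th–95th percentile), against 0.07–0.25 under the planned model. With 8 HV it was 0.09–0.27. The median ratio stayed stable throughout. The HV/pSS direction, which the programming notes for Tables 2.5 and 2.9 give, was not examined.

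The cost is SAP wording, one prior statement in the code and a revised shell, with no new data. With the flat log σ_j prior, intervals for the difference widen by 34–48% with 4 HV and by 12–20% with 8 or 12. They become slightly conservative: coverage is 96.6–97.5% with 4 HV and 95.7–96.7% otherwise.

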#### **Group B: Primary Sjögren's Syndrome Subjects**

Approximately 8 to 12 pSS subjects will be recruited. Due to anticipated greater variability amongst patients, the variability of the imaging parameters will be assessed after approximately 8 subjects have been recruited, and consequently up to an additional 4 subjects may be recruited.

Following a literature review the following information was obtained for the imaging modalities of interest in the parotid glands in different populations. This historical information can be used in the variability assessment as outlined above.

Imaging modality; Parameter	Healthy Volunteers Mean [SD]	Patients (not pSS) Mean [SD] n	Patients (pSS) Mean [SD] n	Reference
$^{18}\text{F}$ -FDG PET; $\text{SUV}_{\text{max}}$	n/a	1.80 [0.53] n=25	n/a	Basu, 2008
$^{18}\text{F}$ -FDG PET; $\text{SUV}_{\text{max}}$	n/a	2.00 [not stated]	2.75 [0.61] n=32	Cohen, 2013
$^{18}\text{F}$ -FDG PET; SUV	n/a	1.90 [0.68] n=78	n/a	Nakamoto, 2005
$^{11}\text{C}$ -MET PET; $\text{SUV}_{\text{max}}$	6.00 [1.5] n=11	n/a	n/a	Isohashi, 2013
DCE MRI, $K_{\text{trans}}$	0.20 [0.04] n=11	n/a	0.26 [0.05] n=21	Roberts, 2008
SD=Standard Deviation				

Using estimates of parameter (this can be any parameter,  $\text{SUV}_{\text{mean}}$ , SUV,  $K_{\text{trans}}$ ) variability, the precision of these estimates calculated as half width of a 95% confidence interval for the mean and expressed as distance from mean to limits, for 4, 8 and 12 subjects has been calculated (Table 5).

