2.7.	Safety	EFF_T4	Point estimate and 95% CI for Multiparametric MRI Derived Parameter of Difference in pSS vs. HV	
Analysed by Parameter and Region of Interest.
 
When applicable for a given ROI, the analysis will be separated by the side of the ROI.
 
Parameters include (median and IQR) Ktrans, D, D*, f, ADC, IRE, ME, and (Mean) lipid content and gland volume as data permits.
 
Summarize Means and Differences (or Ratios) with 95% CI.
 
Note: P value not included as this is not a statistically powered study
	SAC

Pharmacodynamic: Tables					
No.	Population	IDSL / TST ID / Example Shell	Title	Programming Notes	Deliverable [Priority]
2.8.	Safety	EFF_T5	Summary of the Posterior Distribution of the Ratio and Difference of Group Means for Multiparametric MRI Parameter by Region	Paginate by parameter and subject group. Parameters to include but not limited to: Ktrans, ADC, D, and f. For each median values will be analysed. First two columns for ROI and side.	SAC
2.9.	Safety	EFF_T6	Posterior Probability that the Ratio and Difference of Group Means for Multiparametric MRI Parameter Exceeds a Certain Value, by Region	Paginate by parameter and subject group. Parameters to include but not limited to: Ktrans, ADC, D, f and volume. For each median values will be analysed. First two columns for ROI and side. Ratios of interest: 1, 1.5 and 2 Difference of interest: 0 Footnote: Ratio=HV/pSS Note: Values/inequality subject to change based on data	SAC

Note: The above summaries will be generated if data is available.

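### The fixed N(0, 100²) prior in SAP 7.1.3 is vague only for endpoints on a small numerical scale; units for ADC, D and gland volume are not fixed, so on a large scale it could create a group difference in either direction

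*SAP*

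**What the plan says.** SAP 7.1.3 applies a Bayesian comparison of pSS with HV to the endpoints of SAP 7.1.2. The prior for each group mean is a "weakly-informative (vague) conjugate Normal prior density function with mean zero and a large variance", given there as N(0, 100²). Mock shell EFF_T5 in Appendix 12 carries the same prior for both groups (printed as "normal(0, sd = 100"). Of the likelihood, 7.1.3 says "This will have an unknown mean and known variance taken from the raw data", separately for each group.

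The endpoints are the 11C-MET SUV measures and "Multiparametric MRI derived parameters, including but not limited to" Ktrans, D, f and ADC. Gland volume enters the Bayesian set only through the programming note to Table 2.9: "Parameters to include but not limited to: Ktrans, ADC, D, f and volume". Table 2.8 and Figure 2.13 do not name it, and SAP 9.1.2 plans only an ANOVA for it.

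Neither document fixes a unit for ADC, D or volume. SAP 11.3.3 says the sponsor derives no imaging parameters, so values presumably enter as delivered. No rescaling or prior-sensitivity step is planned.

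Group sizes are in Protocol 9.2. For HV: "Approximately 4 to 12 subjects will be recruited", with a "total maximum of approximately 12 subjects for MRI" and a cap of 8 for 11C-MET PET/CT. For pSS: "Approximately 8 to 12 pSS subjects will be recruited". The same section expects patients to vary more than volunteers.

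**The concern.** A prior SD of 100 means nothing until it is set against the scale of the data. If an endpoint is recorded in units that make its standard error comparable with 100, the prior pulls each group mean toward zero. Unless the two groups have the same SD²/n, the pull differs between them and does not cancel in the difference or the ratio. Tables 2.8 and 2.9 and Figure 2.13 could then show a group contrast that comes from the prior, and the same images reported in another unit would give a different posterior probability. The stated aim of the analysis is interpretable probability statements, and such statements should not depend on the unit of measurement.

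**Working it through.** **Plan's own figure.** The SAP gives no posterior or shrinkage figure. The nearest number is Protocol Table 5: the 95% half-width for SD 1 and N = 12 is t(0.975, 11) × 1/√12 = 0.635, which matches the stated 0.64.

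**Formulas.** Normal data with known variance, prior N(0, 100²):

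- weight on the data: w = 100² / (100² + SD²/n)
- posterior mean = w × raw mean; posterior variance = w × SD²/n
- P(pSS>HV) = Φ(difference in posterior means / √(sum of posterior variances))

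**When the prior stops being vague.** Setting w = 0.99 gives SE = 100 × √(1/0.99 − 1) = 10.05. That is an SD of about 20 at n = 4, 28 at n = 8 and 35 at n = 12. A 10% pull needs SE = 33.3.

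**Scales given in Protocol 9.2.**

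- SUVmax 6.00 (SD 1.5): w = 10000/10000.5625 = 0.99994 at n = 4 and 0.99998 at n = 12. Two groups with equal means of 6 would differ by 0.0002.
- Ktrans 0.20 (SD 0.04) in HV and 0.26 (SD 0.05) in pSS: w = 1.000000 in both groups, and the difference stays at 0.06.

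The prior is harmless here. For f the documents give no figure, but as a fraction it is on a small scale too.

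**Large scale (assumed).** Both raw means are 1000, so the true contrast is zero. With SD 200:

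- n = 4: w = 10000/20000 = 0.50, posterior mean 500, posterior SD 70.7
- n = 8: w = 10000/15000 = 0.667, posterior mean 667, posterior SD 57.7
- n = 12: w = 10000/13333 = 0.75, posterior mean 750, posterior SD 50

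| pSS: SD, n | HV: SD, n | Posterior means (pSS, HV) | Difference | P(pSS>HV) |
|---|---|---|---|---|
| 200, 12 | 200, 4 | 750, 500 | +250 | 0.998 |
| 200, 12 | 200, 8 | 750, 667 | +83 | 0.86 |
| 200, 12 | 200, 12 | 750, 750 | 0 | 0.50 |
| 200, 8 | 200, 12 | 667, 750 | −83 | 0.14 |
| 300, 8 | 150, 4 | 471, 640 | −169 | 0.04 |
| 100, 12 | 100, 4 | 923, 800 | +123 | 0.990 |
| 300, 12 | 300, 4 | 571, 308 | +264 | 0.994 |

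For the top row, z = 250/√(2500 + 5000) = 250/86.6 = 2.89. The ratio of posterior means is 750/500 = 1.5, one of the ratio values for which 7.1.3 reports a probability. In the fifth row the larger pSS group is pulled more, because 300²/8 = 11250 exceeds 150²/4 = 5625.

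**Same data, other unit.** Divide the top row by 1000 (mean 1, SD 0.2): the difference is 7 × 10⁻⁷ and P = 0.500.

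**Volume (assumed 25,000, SD 8,000, as if in mm³), 12 v 4.** w = 0.0019 and 0.0006, posterior means 47 and 16, ratio of posterior means 3.0. In mL (25, SD 8) that ratio is 1.001.

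**After rescaling the prior.** With prior SD = 100 × 200 = 20,000, the top row gives posterior means 999.99 and 999.98, a difference of 0.02 and P = 0.500.

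**The case against.** The strongest reply is that nothing in the documents puts any endpoint on a harmful scale. The only scales quoted are an SUV of about 6 and a Ktrans of about 0.2, and the largest SD in Protocol Table 5 is 1.5. The prior may have been chosen with such numbers in mind. This stands, and it makes the point conditional.

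A second reply is that the distortion would be seen. EFF_T5 prints the prior, the σ used and the posterior mean; Table 2.6 gives raw MRI summaries; and the ANOVA in Table 2.7 is untouched by the prior. The study is exploratory, with no hypothesis test and no decision threshold on these probabilities. This limits the harm but does not correct Tables 2.8 and 2.9 or Figure 2.13. The shell for Table 2.9 (EFF_T6) shows only probabilities, so a reader of that table alone has no cue.

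A third reply is the log-Normal fallback in 7.1.3. On the log scale 1000 becomes 6.9 and the prior would be harmless, but the fallback is triggered by the shape of the data, not by the unit.

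A reader might also infer that the pull always falls harder on HV as the smaller group, and so favours a higher pSS value. The documents do not support that. The pull follows SD²/n. For MRI, the only modality where a large scale is plausible, HV may reach about 12 against 8 to 12 pSS, and pSS is expected to be more variable. Where HV is capped at 8, in 11C-MET PET/CT, the SUV scale makes the effect nil.

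**Conclusion.** The point holds as a minor, conditional one. A single prior that takes no account of units is called vague for every endpoint, and that description fails once a group's standard error passes roughly 10. The endpoints exposed are ADC, D and, only if the Table 2.9 note is followed, gland volume. SUV, Ktrans and f are not affected on the scales described.

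If an exposed endpoint were delivered on a scale near 1000 with SD 100 to 300, equal raw means at 12 pSS v 4 HV would give a difference of +123 to +264 with a posterior probability of 0.99 or more. Less extreme splits give less, equal SD²/n gives nothing, and greater pSS variability can reverse the sign. The means and SDs of these large-scale cases are assumptions; the group sizes are within Protocol 9.2. It would be wrong to read this as showing that the planned Bayesian results will be distorted: the documents do not say what units will be used.

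**What to change.** In SAP 7.1.3, take one of these:

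- a flat prior on each group mean;
- a prior SD scaled to the endpoint, for example 100 times its pooled SD. This uses the data weakly to set the prior, but 7.1.3 already takes the variance from the data;
- dividing each endpoint by its pooled SD before PROC MCMC and multiplying back. Do not centre, so that ratios are preserved. This is equivalent to the scaled prior.

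Alternatively, keep the prior and fix a reporting unit for each endpoint such that the standard error is far below 100. ADC, D and volume are the ones that need it.

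Update the prior column of shell EFF_T5 to match. The cost is a sentence or two in the SAP and about a line of code. Results for small-scale endpoints are essentially unchanged.
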